6.1.3. Follow-up Phase

All subjects who complete the study will return for a safety visit 4 weeks after their last study visit to assess the subject’s general health status and assess adverse events, if applicable.

Figure 1: Study Design

7. SELECTION AND WITHDRAWAL OF SUBJECTS

7.1. Clinical Trial Population

The population for this trial will include male and female subjects ≥ 21 and ≤ 65 years of age with a diagnosis of primary or secondary progressive multiple sclerosis who are currently untreated with immunomodulating medications or who are receiving either glatiramer acetate (GA) or interferon beta (IFN β -1a or IFN β -1b) treatment.

It is estimated that in order to complete 250 subjects, approximately 280 subjects will need to be screened.

7.2. Inclusion/Exclusion Criteria

7.2.1. Inclusion Criteria

1. Subject provides written informed consent and is willing and able to comply with the protocol in the opinion of the Investigator.
2. Male or female subjects who are ≥ 21 and ≤ 65 years of age, on the day of signing the informed consent.
3. Confirmed diagnosis of SPMS or PPMS according to 2010 International Panel Criteria
4. Typical MS lesions on MRI according to Swanton's MRI Criteria (at least one lesion in two or more of the following regions: periventricular, juxtacortical, infratentorial [brainstem/cerebellum], spinal cord)
5. EDSS 3.0-6.5, inclusive
6. Clinical evidence of disability progression in the preceding 2 years, as measured by any of the following (excluding progression during clinical relapses):
 - o worsening overall EDSS of at least 0.5 points (may be assessed retrospectively, but cannot be during a clinical relapse)
 - or
 - o 20% worsening in 25-foot walk (25FW)
 - or
 - o 20% worsening in 9-hole peg test (9HPT) in either hand
7. Existing multiple sclerosis pharmacotherapy status may include interferon-beta or glatiramer acetate or none (i.e., untreated).
8. Females of child-bearing potential must have a negative serum β -hCG at screening and must be willing to use appropriate contraception (as defined by the investigator) for the duration of study treatment and 30 days after the last dose of study treatment.
9. Male subjects should practice contraception as follows: condom use and contraception by female partner.
10. Subject is in good physical health on the basis of medical history, physical examination, and laboratory screening, as defined by the investigator.

11. Subject is willing and able to comply with the protocol assessments and visits, in the opinion of the study nurse/coordinator and the Investigator.

7.2.2. Exclusion Criteria

Note: If any laboratory exclusion criteria are outside the normal range, the site may have the subject retested. If upon retesting the value remains outside the normal range, the significance of this value must be discussed with the Medical Safety Monitor for enrollment consideration.

1. Progressive neurological disorder other than SPMS or PPMS
2. Relapse and/or systemic corticosteroid treatment within 3 months of screening. Inhaled or topical steroids are allowed.
3. Current use of intermittent systemic corticosteroids (i.e., monthly or bimonthly intravenous methylprednisolone).
4. Use of oral immunosuppressants (e.g., azathioprine, methotrexate, cyclosporine, teriflunomide [Aubagio[®]]) within 6 months of screening
5. Use of mitoxantrone, natalizumab, or IVIg within 6 months of screening, or use of alemtuzumab within the prior 10 years
6. Use of fingolimod or dimethyl fumarate [Tecfidera[®]] within 3 months of screening
7. Use of rituximab or other B-cell therapy within 12 months of screening
8. Current use of other MS disease-modifying treatments (DMTs) besides glatiramer acetate, IFN β -1 (any formulation) and the above listed medications.
9. Current use of cimetidine, cyclosporine, dronedarone, lopinavir, probenecid, quinidine (including Neudexta), ranolazine, rifampin, ritonavir, or tipranavir.
10. Subject has clinically significant cardiovascular disease, including myocardial infarct within last 6 months, unstable ischemic heart disease, congestive heart failure or angina.
11. Subject has a resting pulse < 50 bpm, SA or AV block (Type II or greater), uncontrolled hypertension, or QTcF > 450 ms
12. Clinically significant pulmonary conditions, including severe COPD, fibrosis, or tuberculosis
13. Subject demonstrates evidence of acute hepatitis, clinically significant chronic hepatitis, or evidence of clinically significant impaired hepatic function through clinical and laboratory evaluation including ALP > 1.5x ULN; ALT or AST > 2x ULN; GGT > 3x ULN
14. Immune system disease (other than multiple sclerosis and autoimmune thyroid disease)
15. Subject has a history of stomach or intestinal surgery or any other condition that could interfere with or is judged by the Investigator to interfere with absorption, distribution, metabolism, or excretion of study drug.
16. Subject has any abnormal laboratory parameter at screening that indicates a clinically significant medical condition as determined by the Investigator or has any of the following abnormalities at screening:
 - Creatinine: females > 0.95 mg/dL; males > 1.17 mg/dL
 - WBCs < 3,000 mm³
 - Lymphocytes < 800 mm³
 - Platelets < 90,000 mm³

17. Subject has a history of malignancy < 5 years prior to signing the informed consent, except for adequately treated basal cell or squamous cell skin cancer or *in situ* cervical cancer
18. History of HIV, clinically significant chronic hepatitis, or other active infection
19. Subject currently has a clinically significant medical condition (other than MS) including the following: neurological, metabolic, hepatic, renal, hematological, pulmonary, cardiovascular (including uncontrolled hypertension), gastrointestinal, urological disorder, or central nervous system (CNS) infection that would pose a risk to the subject if they were to participate in the study or that might confound the results of the study.

Note: Active medical conditions that are minor or well-controlled are not exclusionary if, in the judgment of the Investigator, they do not affect risk to the subject or the study results. In cases in which the impact of the condition upon risk to the subject or study results is unclear, the Medical Safety Monitor should be consulted. Any subject with a known cardiovascular disease or condition (even if controlled) must be discussed with the Medical Safety Monitor before being screened.

20. Subjects with moderate to severe depression as determined by the Beck Depression Inventory-Fast Screen (BDI-FS).
21. Subject has a history of alcohol or substance abuse (DSM-IV-TR criteria) within 3 months prior to screening or alcohol or substance dependence (DSM-IV-TR criteria) within 12 months prior to screening. The only exceptions include caffeine or nicotine abuse/dependence.
22. Subject has poor peripheral venous access that will limit the ability to draw blood as judged by the Investigator.
23. Subject is currently participating, or has participated in, a study with an investigational or marketed compound or device within 3 months prior to signing the informed consent.
24. Subject is unable to cooperate with any study procedures, unlikely to adhere to the study procedures and keep appointments, in the opinion of the Investigator, or was planning to relocate during the study.
25. Subject is unable to undergo MRI imaging because of having an artificial heart valve, metal plate, pin, or other metallic objects (including gun shots or shrapnel) in their body or is unable to complete all the five MRI scans required for this study.
26. Subject is unable to lie sufficiently still in an MRI to obtain a high quality MRI image.

Additional Exclusion Criteria for Lumbar Puncture Sub-Study

The following additional exclusion criteria apply to subjects electing to enroll in the lumbar puncture sub-study:

27. A clinical history of a bleeding disorder.
28. Current treatment with blood thinner medications such as warfarin (Coumadin), or clopidogrel (Plavix), dipyridamole (Persantine), ticlopidine (Ticlid), warfarin, heparin, although aspirin is allowed.

7.3. Subject Withdrawal/Discontinuation Criteria

Subjects may request to be withdrawn from the study at any time for any reason.

The Investigator may interrupt the treatment of any subject whose health or well-being may be compromised by continuation in this study. The following instances may require subjects to be withdrawn from the study:

- Subject fails to adequately comply with the dosing, evaluations, or other requirements of the study at the discretion of Investigator;
- Subjects who have adverse events that require discontinuation of study medication;
- Subjects who, in the opinion of the Investigator, should be discontinued for their well-being;
- Subjects who are no longer able to understand task instructions or to perform tests adequately;
- Subject becomes pregnant during the study. See section 11.8 for reporting requirements and follow-up of the pregnancy;
- Any Grade 3 or higher CTCAE;
- Abnormal laboratory values as described in section 8.6.2.

If a subject withdraws or is removed from the study for any reason, the reason and date of discontinuation of study medication should be recorded in the appropriate section of the Case Report Form (CRF). At the time of study discontinuation, every effort should be made to ensure all Early Withdrawal (EW) procedures and evaluations are performed.

The study sponsors reserve the right to discontinue the study at any time for medical or administrative reasons.

Study drug re-administration may be considered as noted below.

7.3.1. Follow-up Procedures Upon Discontinuation/Withdrawal

If a subject discontinues study medication for any reason, the subject will be encouraged to continue to be followed within the study, but on a reduced study visit schedule. Depending upon when the subject discontinued study drug, the reduced study visit schedule will include study visits at Week 24, 48, 72, and 96. The timing of all study visits will remain relative to the original baseline date. For subjects who discontinue study drug between regularly scheduled study visits, the subject should complete the next regularly scheduled study visit after study drug discontinuation, and then shift to the reduced study visit schedule. For subjects who discontinue study drug at a regularly scheduled study visit, the subject should shift immediately to the reduced study visit schedule. For subjects discontinuing study drug but remaining in the study for follow-up, study visits will occur on an approximate semi-annual basis until Week 96. Table 2 outlines the procedures and assessments to be conducted in subjects remaining in the study for follow-up but are off study medication. After study drug discontinuation, new-onset AEs will not be collected.

If a subject discontinues/withdraws prior to study completion and does not wish to continue follow-up within the study (i.e. return for semi-annual visits), then all assessments scheduled for the Early Withdrawal visit (Table 2) should be performed at the time of study discontinuation.

A termination CRF page should be completed for every subject who received study medication whether or not the subject completed the study. The reason for discontinuation should be indicated on the CRF. Any AEs that are present at the time of discontinuation/ withdrawal should be followed in accordance with the safety requirements outlined in Section 11.

For all subjects who complete the study on study medication, a follow-up visit (Week 100) will be conducted 4 weeks after the last visit to assess general health and adverse event status.

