8.8.2.12. Adverse Event (AE) Monitoring

The CSSPI or a qualified designee listed on Form FDA 1572 must assess the severity and relationship to study medication for all AEs (see Section 11.3).

All observed or volunteered AEs regardless of treatment group or suspected causal relationship to the investigational product(s) will be recorded on the AE page(s) of the CRF.

Each CSSPI and research team are responsible for identifying adverse events and reporting them through the DCC Online Adverse Event Reporting System.

For all AEs, the Investigator must pursue and obtain information adequate to determine the outcome of the AE and to assess whether it meets the criteria for classification as an SAE (see Section 11.3) requiring immediate notification to the Sponsor or its designated representative.

For all AEs, sufficient information should be obtained by the Investigator to determine the causality of the AE. The Investigator is required to assess causality and indicate that assessment on the CRF. For AEs with a causal relationship to the investigational product, follow-up by the Investigator is required until the event or its sequelae resolve or stabilize at a level acceptable to the Investigator, and Sponsor concurs with that assessment.

Adverse events (serious and non-serious) including all suspected unexpected serious adverse reactions (SUSARs) should be recorded on the CRF from the date of informed consent until the end of their participation in the study (i.e., the subject has discontinued or completed the follow-up visit).

The DCC will prepare aggregate reports of all adverse events (serious/not serious, expected/unexpected and relationship to study drug) for the Independent Medical Monitor (IMM) on a quarterly basis and the DSMB on a semi-annual basis, or as requested by either the Independent Medical Safety Monitor or the DSMB. In addition, all adverse events will be coded using the Medical Dictionary for Regulatory Affairs (MedDRA) system. A separate report detailing protocol compliance will also be available from the DCC for DSMB as requested.

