11.4. Recording Adverse Events

Adverse events should be collected and recorded for each subject from the date the informed consent form (ICF) was signed until the end of their participation in the study, (i.e., the subject has discontinued or completed the study) through the follow-up visit with the exception of those subjects who discontinue study medication during the study and are followed on a semi-annual basis. Subjects who discontinue study medication but continue follow-up within the study will not have AEs collected after study drug discontinuation. Only those AEs that occurred while on study drug that have not been resolved will be followed until resolution or stabilization.

Following the end of the subject’s participation in the study, the CSSPI or an authorized delegate should report SAEs “spontaneously” if considered at least possibly related to study medication.

Adverse events may be volunteered spontaneously by the study subject, or discovered by the study staff during physical examinations or by asking an open, non-leading question such as, “How have you been feeling since you were last asked?” All AEs and any required remedial action will be recorded in the subject’s source documentation and transcribed onto the appropriate CRF page for the study period indicated. The nature of AE, date (and time, if known) of AE onset, date (and time, if known) of AE outcome to date, severity, and action taken of the AE will be documented together with the CSSPIs or an authorized physician’s assessment of the seriousness of the AE and causal relationship to study medication and/or study procedure (at the time of assessment).

All AEs should be recorded individually in the study subject’s own words (verbatim) unless, in the opinion of the PI or an authorized physician, the AEs constitute components of a recognized condition, disease, or syndrome. In the latter case, the condition, disease, or syndrome should be named rather than each individual symptom. The AEs will subsequently be coded using the MedDRA.

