11.6.1. SAE Reporting Requirements

The CSSPI or an authorized delegate is responsible for submitting the requested information via the DCC Online Adverse Event Reporting System within 24 hours or as soon as possible after learning of the event. Following the end of the subject's participation in the study, the CSSPI or an authorized delegate should report SAEs "spontaneously" if considered at least possibly related to study medication. Upon entry of a serious adverse event by a CSSPI, the DCC Online Adverse Event Reporting System will immediately notify the Medical Safety Monitor (MSM).

- Within **24 hours** (of learning of the event), investigators must report any Serious Adverse Events (SAEs). Investigators must report all other AEs within **5 working days/7 calendar days** (of learning of the event).

Serious adverse events: The CSSPI determines causality (related, probably related, possibly related, unlikely to be related, and unrelated) of the adverse event. The IMM will review the SAE report. The IMM may request further information if necessary. The Online Adverse Event Reporting System maintains audit trails and stores data (and data updated) and communication related to any adverse event in the study. The IMM may determine that the Serious Adverse Event requires expedited reporting to the Sponsor and FDA (Food and Drug Administration). The DCC will prepare a Medwatch safety report for submission to the FDA. If warranted, the IMM will notify the DSMB chair. The DSMB may suggest changes to the protocol or consent form to the Study Chair as a consequence of adverse events.

As a minimum requirement, the initial notification will provide the following information:

- Subject ID number
- Date of SAE onset
- An event term
- Details of SAE (if sufficient information is available)
- Criterion/criteria for classification as “serious”
- Causality assessment (if sufficient information is available to make this classification).

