Subjects who prematurely discontinue study medication will continue to be followed on a semi-annual basis until the end of the study. For such subjects, adverse events will not be collected post study drug discontinuation. Existing AEs will be followed until the AE resolves or stabilizes.

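### New AEs go uncollected once a subject stops study drug but stays in follow-up, while the SAP rate model still counts that subject's off-drug time

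*Combined protocol and SAP*

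**What the plan says.** The no-collection rule is current text in both documents. Protocol 7.3.1 reads: "After study drug discontinuation, new-onset AEs will not be collected". Protocol 11.4 reads: "Subjects who discontinue study medication but continue follow-up within the study will not have AEs collected after study drug discontinuation". SAP section 1 reads: "For such subjects, adverse events will not be collected post study drug discontinuation". The Synopsis, Table 1 footnote 8, Protocol 8.8.2.8, and SAP 10.1 agree. AEs already present at stopping are followed; new ones are not recorded. None of these places exempts SAEs.

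These subjects remain in the trial: under Protocol 7.3.1, "study visits will occur on an approximate semi-annual basis until Week 96". The Table 2 column for those visits keeps MRI, OCT, EDSS and the questionnaires. It has no AE review, vital signs, clinical laboratory tests or ECG.

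On-drug completers are treated differently: "For all subjects who complete the study on study medication, a follow-up visit (Week 100) will be conducted 4 weeks after the last visit", and its stated purpose includes adverse event status.

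For the analysis, SAP 7.2.1 compares the percentage of subjects with an event and also fits a Poisson model for the event rate. The exposure term T_i in that model runs from randomization to last follow-up.

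**The concern.** Safety and tolerability form a primary objective, and subjects who stop drug are the group in whom delayed or serious events most need to be seen. Here observation ends on the day the drug stops, while subjects who tolerated the drug are observed four weeks longer. A stopper may attend up to four more visits without being asked about a new SAE.

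The safety net after participation covers SAEs "if considered at least possibly related to study medication" (Protocol 11.6.1). It starts only when participation ends, so it does not reach someone who is off drug and still attending.

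The analysis then treats the unobserved months as if they had been observed and event-free. That lowers the estimated rate in each arm, and lowers it more in the arm with more stopping.

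**Working it through.** The plan gives no figure on this point. Its only safety figure is the power for a 15-point difference (SAP 9.2), and nothing here rests on it.

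**1. The texts side by side**

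- *No new AEs after stopping:* Protocol Synopsis, Table 1 footnote 8, 7.3.1, 8.8.2.8 and 11.4; SAP 1 and 10.1.
- *Any SAE to be reported within 24 hours of learning of it, with no off-drug exemption:* Protocol 11.6.1.
- *Events in post-treatment follow-up count as AEs to be recorded:* Protocol 11.2 and SAP 2.2.
- *AEs recorded* "from the date of informed consent until the end of their participation in the study": Protocol 8.8.2.12. The sentence goes on to explain the end of participation as having discontinued or having completed the follow-up visit, so it is ambiguous for a subject who is off drug but attending.
- *Who has the four-week visit:* all study completers in Protocol 6.1.3, but only those completing on drug in the Synopsis, Protocol 7.3.1 and SAP 1.

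A site that learns of a new SAE in an off-drug subject is told both to report it and not to collect it.

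**2. What the missing four-week window costs one stopper**

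For a stop at week t, the uncollected share of on-drug time plus four weeks is 4/(t+4):

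- Week 8: 4/12 = 33%
- Week 24: 4/28 = 14%
- Week 48: 4/52 = 8%

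**3. What T_i does to the rate**

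Let d be the share of an arm that stops at week t and stays to Week 96. A stopper has t weeks of AE collection but contributes 96 weeks to T_i. An on-drug completer has 100 weeks of both. With one constant event rate, the estimated rate equals the true rate multiplied by

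F = [d·t + (1−d)·100] / [d·96 + (1−d)·100]

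The values of d and t below are assumptions. The documents give only an overall 10% dropout allowance (Protocol 12.1.3, SAP 9.1) and 86% two-year completion at 60 mg/d in an earlier trial (Protocol 4.6.3). Neither is a stopping rate by arm for this trial.

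| Stop week | F at d = 10% | F at d = 20% | Ratio multiplier (20% active, 10% placebo) |
|---|---|---|---|
| 48 | 94.8/99.6 = 0.952 | 89.6/99.2 = 0.903 | 0.949 |
| 24 | 92.4/99.6 = 0.928 | 84.8/99.2 = 0.855 | 0.921 |
| 8 | 90.8/99.6 = 0.912 | 81.6/99.2 = 0.823 | 0.902 |

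- *Equal stopping of 10%:* both rates are 5% to 9% too low, and the ratio is unchanged.
- *10% placebo, 20% active:* a true ratio of 1.5 appears as 1.42 to 1.35.
- *20% placebo, 10% active:* the multiplier reverses to 0.952/0.903 = 1.05 up to 0.912/0.823 = 1.11.

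**4. After correction**

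If T_i covers only time under AE collection, numerator and denominator refer to the same weeks. F is then 1.00 in each arm.

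**5. What the four-week window adds to the percentages**

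For a 100-week risk p, take the hazard λ = −ln(1−p)/100. The observed risk is (1−d)·p + d·(1−e^(−λt)). With p = 30%, d = 30% and t = 8 (all assumed), λ = 0.003567:

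- Without the window: 0.7×0.30 + 0.3×0.0281 = 21.8%.
- With the window (t = 12): 0.7×0.30 + 0.3×0.0419 = 22.3%.

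The gain is under 0.5 points. Most of the uncollected time is the longer off-drug follow-up to Week 96.

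**The case against.** The rule is deliberate and stated consistently. The endpoints are treatment-emergent events, with treatment-related AEs of primary interest (SAP 2.2), and events months after the last dose are not clearly either. Harm that leads to stopping is already captured in three ways: the tolerability endpoints count discontinuation due to AEs, AEs present at stopping are followed, and a subject who stops between visits attends the next regular visit before moving to the reduced schedule.

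Much of this stands, and it rules out three stronger readings that a reader might infer.

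- *That the percentage with any AE is biased because subjects who stop for an AE go on to have more.* Such a subject is already counted as having at least one event, so later events change nothing. The percentages remain exposed for SAEs and for individual system organ classes, where the event that led to stopping may not be the one missed.
- *That harm is under-counted in the active arm in particular.* No stopping rates by arm are given. Under the constant-rate model, equal stopping leaves the rate ratio unshifted.
- *That Protocol 8.8.2.12 lays down the reverse rule.* Its sentence allows collection to end at discontinuation, so it is ambiguous rather than opposed.

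The objection does not answer the conflict over SAEs, the absence of any post-dose window for stoppers when completers have one, or the mismatch between T_i and the collection period. SAP 2.2 sets no limit after the last dose that would justify ending collection at that dose.

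**Conclusion.** The point holds in three parts. First, subjects who stop drug and stay in follow-up have no new-onset AE collection, so new SAEs and delayed events can be missed; this follows directly from the text. Second, the sections on SAEs, post-treatment events and the four-week visit do not agree and must be reconciled. Third, T_i includes months without AE collection, so event rates are understated whenever anyone stops and stays.

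A bias between arms is conditional on unequal stopping, and its direction depends on which arm stops more. With an assumed 10% on placebo and 20% on active, the rate ratio is multiplied by about 0.95 (stops at Week 48) to 0.90 (Week 8). This rests on one constant event rate, common to stoppers and completers, and on stoppers staying to Week 96. If the event rate falls after stopping, the understatement relative to the true rate over all follow-up is smaller.

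**What to change.** - **Collection.** In Protocol 7.3.1, 8.8.2.8 and 11.4 and SAP 10.1, for subjects who stop drug but stay in the study: collect new AEs for the same four weeks after the last dose that completers have, asked at the next scheduled visit. Collect new SAEs at each remaining semi-annual visit.
- **Table 2.** Add *Adverse event review* to the column for visits after drug discontinuation.
- **SAP 7.2.1.** Define T_i as the time under AE collection for the event type analysed: to four weeks after the last dose for all AEs, and to the last visit at which SAEs were asked about for SAEs. That section introduces the model for treatment-related AEs but defines the count as SAEs, so the event type should be stated.
- **Reconciliation.** Align the Synopsis, the Table 1 and Table 2 notes, Protocol 6.1.3, 7.3.1, 8.8.2.8, 8.8.2.12, 11.2, 11.4 and 11.6.1, and SAP 1, 2.2 and 10.1.

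The cost is a few extra questions and some data entry at visits already scheduled, plus wording changes. Two limits remain. Semi-annual visits are 24 weeks apart, so some four-week windows will rely on recall. Percentages with any AE will still cover unequal observation time, and the report should say so.
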